13.6. Subject Confidentiality

The Investigator must ensure that subjects' privacy is maintained. On the eCRF or other documents submitted to the Sponsor, subjects will be identified by a subject number or a subject number and initials only. Documents that are not submitted to the Sponsor (e.g., signed informed consent documents) should be kept in a strictly confidential file by the Principal Investigator.

The Investigator shall permit authorized representatives of the Sponsor, regulatory authorities and IECs to review the portion of the subject's medical record that is directly related to the study. As part of the required content of informed consent documents, the subject must be informed that his/her records will be reviewed in this manner.

13.7. Disclosure of Information

Information concerning the study, patent applications, processes, scientific data or other pertinent information is confidential and remains the property of the Sponsor. The Principal Investigator may use this information for the purposes of the study only.

It is understood by the Principal Investigator that the Sponsor will use information obtained in this clinical study in connection with the clinical development program, and therefore may disclose it as required to other clinical Investigators and to regulatory authorities. In order to allow the use of the information derived from this clinical study, the Principal Investigator understands that he/she has an obligation to provide complete test results and all data obtained during this study to the Sponsor.

Verbal or written discussion of results prior to study completion and full reporting should only be undertaken with written consent from the Sponsor.

APPENDIX B: MINI-MENTAL STATE EXAM (ABBREVIATED MENTAL TEST SCORE)

The following questions are put to the patient. Each question correctly answered scores one point. A score of 8 or less suggests cognitive impairment at the time of testing, although further and more formal tests are necessary to confirm a diagnosis of dementia, delirium or other causes of cognitive impairment.

Question	Score
What is your age? (1 point)	
What is the time to the nearest hour? (1 point)	
Give the patient an address, and ask him or her to repeat it at the end of the test. (1 point) e.g. 42 West Street	
What is the year? (1 point)	
What is the name of the office or doctor you are seeing today? (1 point)	
Can the patient recognize two persons (the doctor, nurse, home help, etc.)? (1 point)	
What is your date of birth? (day and month sufficient) (1 point)	
In what year was the 9-11 terrorist attack? (1 point) (other dates can be used, with a preference for dates some time in the past.)	
Name the present president of the USA. (1 point)	
Count backwards from 10 down to 1. (1 point)	

APPENDIX C: PSI (PORT SCORE)

The Pneumonia Severity Index (PSI) algorithm is detailed below. An online, automated PSI calculator is available on the US Agency for Healthcare Research and Quality website.

Step 1: Stratify to Risk Class I vs. Risk Classes II-V	
Presence of:	
Over 50 years of age	Yes/No
Altered mental status	Yes/No
Pulse \geq 125/minute	Yes/No
Respiratory rate $>$ 30/minute	Yes/No
Systolic blood pressure $<$ 90 mm Hg	Yes/No
Temperature $<$ 35 °C or \geq 40 °C	Yes/No
History of:	
Neoplastic disease	Yes/No
Congestive heart failure	Yes/No
Cerebrovascular disease	Yes/No
Renal disease	Yes/No
Liver disease	Yes/No
If any "Yes", then proceed to Step 2	
If all "No" then assign to Risk Class I	
Step 2: Stratify to Risk Class II vs III vs IV vs V	
Demographics	Points Assigned
If Male	+Age (yr)
If Female	+Age (yr) - 10
Nursing home resident	+10
Comorbidity	
Neoplastic disease	+30
Liver disease	+20
Congestive heart failure	+10
Cerebrovascular disease	+10
Renal disease	+10
Physical Exam Findings	
Altered mental status	+20
Pulse \geq 125/minute	+10
Respiratory rate $>$ 30/minute	+20

Systolic blood pressure <90 mm Hg	+20
Temperature <35 °C or ≥40 °C	+15
Lab and Radiographic Findings	
Arterial pH <7.35	+30
Blood urea nitrogen ≥30 mg/dl (9 mmol/liter)	+20
Sodium <130 mmol/liter	+20
Glucose ≥250 mg/dl (14 mmol/liter)	+10
Hematocrit <30%	+10
Partial pressure of arterial O ₂ <60mmHg	+10
Pleural effusion	+10
Σ <70 = Risk Class II	
Σ 71-90 = Risk Class III	
Σ 91-130 = Risk Class IV	
Σ >130 = Risk Class V	

APPENDIX D: SOFA SCORE

The SOFA score is assessed as below (source: [Singer et al, 2016](#)).

Table 1. Sequential [Sepsis-Related] Organ Failure Assessment Score^a

System	Score				
	0	1	2	3	4
Respiration					
PaO ₂ /Fio ₂ , mm Hg (kPa)	≥400 (53.3)	<400 (53.3)	<300 (40)	<200 (26.7) with respiratory support	<100 (13.3) with respiratory support
Coagulation					
Platelets, ×10 ³ /μL	≥150	<150	<100	<50	<20
Liver					
Bilirubin, mg/dL (μmol/L)	<1.2 (20)	1.2-1.9 (20-32)	2.0-5.9 (33-101)	6.0-11.9 (102-204)	>12.0 (204)
Cardiovascular					
	MAP ≥70 mm Hg	MAP <70 mm Hg	Dopamine <5 or dobutamine (any dose) ^b	Dopamine 5, 1-15 or epinephrine ≤0.1 or norepinephrine ≤0.1 ^b	Dopamine >15 or epinephrine >0.1 or norepinephrine >0.1 ^b
Central nervous system					
Glasgow Coma Scale score ^c	15	13-14	10-12	6-9	<6
Renal					
Creatinine, mg/dL (μmol/L)	<1.2 (110)	1.2-1.9 (110-170)	2.0-3.4 (171-299)	3.5-4.9 (300-440)	>5.0 (440)
Urine output, mL/d				<500	<200

Abbreviations: Fio₂, fraction of inspired oxygen; MAP, mean arterial pressure; PaO₂, partial pressure of oxygen.

^a Adapted from Vincent et al.²⁷

^b Catecholamine doses are given as μg/kg/min for at least 1 hour.

^c Glasgow Coma Scale scores range from 3-15; higher score indicates better neurological function.

**SUMMARY OF CHANGES FROM SAP VERSION 1.0**

**Section 11.2.2 page 25, the following text has been added:**

Additionally, counts (%) of number subjects with values out of normal range at each scheduled time point will also be presented along with shift tables that will represent the changes in normal range categories across post-baseline time points.

**Section 17, the following tables have been added:**

No.	Title	Analysis Population
14.3.4.1.2.1	SD: Summary of CBC Shifts from Baseline (Low, Normal, High)	Safety
14.3.4.1.2.2	MAD: Summary of CBC Shifts from Baseline (Low, Normal, High)	Safety
14.3.4.2.2.1	SD: Summary of Coagulation Shifts from Baseline (Low, Normal, High)	Safety
14.3.4.2.2.2	MAD: Summary of Coagulation Shifts from Baseline (Low, Normal, High)	Safety
14.3.4.3.2.1	SD: Summary of Comprehensive Metabolic Profile Shifts from Baseline (Low, Normal, High)	Safety
14.3.4.3.2.2	MAD: Summary of Comprehensive Metabolic Profile Shifts from Baseline (Low, Normal, High)	Safety

**Section 18, the following listings have been added:**

No.	Title	Analysis Population
16.2.8.1.2.1	SD: Abnormal CBC	Intent-to-Treat
16.2.8.1.2.2	MAD: Abnormal CBC	Intent-to-Treat
16.2.8.2.2.1	SD: Abnormal Coagulation	Intent-to-Treat
16.2.8.2.2.2	MAD: Abnormal Coagulation	Intent-to-Treat
16.2.8.3.2.1	SD: Abnormal Comprehensive Metabolic Profile	Intent-to-Treat
16.2.8.3.2.2	MAD: Abnormal Comprehensive Metabolic Profile	Intent-to-Treat

**List of Abbreviations**

Abbreviation	Description
AUC 0-t	The area under the plasma concentration-time curve, from time 0 (time of dosing) to the last time point with measurable analyte concentration, calculated by the log down, linear up trapezoidal method.
AE	Adverse Event
ATC	Anatomical Therapeutic Class
AUC 0-inf	The area under the plasma concentration-time curve from time 0 extrapolated to infinity. AUC 0-inf is calculated as the sum of AUC 0-t plus the ratio of the last measurable plasma concentration to the elimination rate constant ( $k_{el}$ ).
AUC 0-8	The area under the plasma concentration-time curve, from time 0 (time of dosing) to the 8 hours concentration, calculated by the log down, linear up trapezoidal method.
BLQ	Below the quantitation limit
CAP	Community-Acquired Pneumonia
CBC	Complete Blood Count
C max	Maximum observed concentration
C min	Minimum observed concentration over the dosing interval.
CL/F	Apparent clearance calculated as Dose/AUC 0-inf .
CS	Clinically Significant
CSR	Clinical Study Report
CV	Coefficient of variation
DLT	Dose Limiting Toxicity
DN_AUC 0-inf	Dose-normalized AUC 0-inf , calculated as AUC 0-inf divided by dose.
DN_AUC 0-t	Dose-normalized AUC 0-t , calculated as AUC 0-t divided by dose.
DN_AUC 0-8	Dose-normalized AUC 0-8 , calculated as AUC 0-8 divided by dose.
DN_C max	Dose-normalized C max , calculated as C max divided by dose.
EKG	Electrocardiogram
eCRF	Electronic Case Report Form
EOS	End of Study
GCP	Good Clinical Practice
geo CV	Geometric Coefficient of Variation
HIV	Human Immunodeficiency Virus
ITT	Intention-to-treat
IV	Intravenous
IWRS	Interactive web response system
k el	Apparent terminal elimination rate constant, calculated by linear regression of the terminal linear portion of the log concentration vs. time curve.
LLQ	Lower Limit of Quantification
MAD	Multiple-Ascending Dose
MedDRA	Medical Dictionary for Regulatory Activities
MMSE	Mini-Mental State Exam
N/A	Not Applicable
NCS	Not Clinically Significant

Abbreviation	Description
NK	Not Known
PE	Physical Examination
PI	Principal Investigator
PK	Pharmacokinetic
PP	Per Protocol
PSI	Pneumonia Severity Index
PT	Preferred Term
rhu-pGSN	Recombinant human plasma Gelsolin
SAE	Serious Adverse Event
SAP	Statistical Analysis Plan
SD	Single Dose
SD*	Standard Deviation
S.I.	International System of Units
SOC*	Standard of Care
SOC	System Organ Class
SOP	Standard Operating Procedure
$t_{1/2}$	Apparent elimination half-life, calculated as $\ln(2)/k_{el}$ .
TEAE	Treatment Emergent Adverse Event
$T_{max}$	Time to maximum observed drug concentration. If the maximum value occurs at more than one time point, $T_{max}$ is defined as the first time point with this value.
$V_z/F$	Apparent volume of distribution at the terminal phase, calculated as $Dose / (k_{el} \times AUC_{0-inf})$ .
WHO-DD	World Health Organization Drug Dictionary

## **1. INTRODUCTION**

The following Statistical Analysis Plan (SAP) provides the outline for the statistical analysis of the data from the BT-201 study.

The planned analyses identified in this SAP may be included in clinical study reports (CSRs), regulatory submissions, or future manuscripts. Also, post hoc exploratory analyses not necessarily identified in this SAP may be performed to further examine study data. Any post hoc, or unplanned, exploratory analyses performed will be clearly identified as such in the final CSR.

## **2. PROJECT OVERVIEW**

### **2.1 Study Design**

Study BTI-201 is a Phase 1b/2a, double-blind, placebo-controlled, dose-escalation study to evaluate the safety, Pharmacokinetics (PK) and Pharmacodynamics (PD) of recombinant human plasma gelsolin (rhu-pGSN) added to standard of care (SOC\*) in subjects hospitalized for acute community-acquired pneumonia (CAP). Each dosing cohort will include 8 subjects randomized 3:1 rhu-pGSN:placebo (6 rhu-pGSN subjects:2 placebo subjects).

There will be 1 single dose cohort (Cohort 1) and 3 multiple dose cohorts (Cohorts 2, 3 and 4).

Dose will be based on actual body weight. Dose escalation will involve 3 dose levels of rhu-pGSN (6, 12, and 24 mg/kg) in patients admitted for CAP. Dose escalation will only occur after post-therapy safety information on all subjects in the prior cohort has been reviewed at Day 7 for the single-dose (SD) and multiple-ascending dose (MAD\*) arms.

The MAD portion of the study will commence once single doses of 6 mg/kg of rhu-pGSN are shown to be acceptably safe. The first 2 doses must be administered in the hospital, but the third dose can be given in a monitored outpatient setting where appropriate.

Discharged subjects will return for follow-up 7 days after the initiation of therapy (Day 7) and on Day 28 for the End-of-Study (EOS) Visit.

To assess safety and tolerability, subjects will undergo physical examinations (PE; including vital sign measurements), AE assessments, concomitant medication assessments, safety laboratory testing and Electrocardiogram (EKGs - completed locally), and other testing as per local custom.

### **2.2 Objectives**

#### **2.2.1 Primary objective**

The primary objective of the study will be to evaluate the safety and tolerability of single and multiple ascending doses of rhu-pGSN administered by once-daily intravenous (IV) push to hospitalized subjects with a primary admitting diagnosis of CAP.

#### **2.2.2 Secondary objectives**

The secondary objective of the study will be to characterize the PK profile of rhu-pGSN after single or multiple IV doses

#### **2.2.3 Exploratory objective.**

The exploratory objectives of the study will be to investigate the following:

- To assess the quantitative relationship of pGSN levels at baseline with clinical outcomes, changes in prognostic indices and inflammatory biomarkers, and etiologic pathogen type.
- To assess the relationship between rhu-pGSN dose and clinical response and changes in surrogate biomarkers of efficacy.

#### **2.2.4 Immunogenicity objective.**

The immunogenicity objective of the study will be to investigate the post-treatment development of antibodies against rhu-pGSN by Day 28.

### 2.3 Sample Size

The sample size of N=6 rhu-pGSN recipients per dose level and combined placebo in the SD and MAD portions of the trial were chosen based on limiting exposure to pGSN in this initial study in the current development program. The sample sizes in this trial have the following properties in relation to interpretation of Adverse Events (AEs) incidence rates (Table 1).

Table 1 presents the Minimum Sample Size such that there is 90% probability of observing at least 1 AE of a certain type if the TRUE underlying AE rate.

**Table 1: Minimum Sample Size Calculations**

Sample Size	TRUE underlying AE rate
6 (each pGSN dose level)	32%
8 (pooled placebo)	21%
24 (pooled pGSN)	10%

With each sample size presented in the table above, if zero AEs of a certain type are observed, one could be "90% confident" the TRUE underlying rate for that AE is at most the rate indicated above.

### 2.4 Randomization

Following screening, subjects qualified for study entry will be randomized to receive rhu-pGSN or placebo during the treatment period. Randomization will be done centrally using the Interactive web response system (IWRS). All eligible subjects will be assigned a randomization number.

There will be 1 single dose cohort (Cohort 1) and 3 multiple dose cohorts (Cohorts 2, 3 and 4). Eight subjects will be sequentially randomized to each cohort for a total number randomized of 32 subjects.

Subjects will be randomized in a 3:1 ratio to rhu-pGSN or placebo (6 rhu-pGSN subjects:2 placebo subjects).

The investigational site team and the subject will be kept blinded to the treatment allocation of each participant. Only the designated pharmacist(s) will be unblinded to the treatment allocation. The unblinded pharmacist will utilize the IWRS system to randomly assign a treatment allocation. The treatment allocation will be available to the unblinded pharmacist(s).

### 3. STATISTICAL CONSIDERATIONS

Data will be handled and processed per the sponsor's representative (Novotech) Standard Operating Procedures (SOPs), which are written based on the principles of good clinical practice (GCP).

All data collected on the eCRFs will be presented in the data listings and will be listed and sorted by SD/MAD, treatment, subject number and visit, where applicable. All summaries will present the data by SD/MAD (apart from PK summaries), treatment group and overall (total subjects), as applicable. In addition, all placebo subjects will be combined into a single placebo group for purposes of summarizing the data.

- Continuous variables: Descriptive statistics will include the number of non-missing values (N), mean, standard deviation (SD\*), median, minimum, maximum.  
  
The minimum and maximum values will be displayed to the same decimal precision as the source data, the arithmetic mean, SD\* and median values will be displayed to one more decimal than the source data for the specific variable.  
  
The appropriate precision for derived variables will be determined based on the precision of the data on which the derivations are based, and statistics will be presented in accordance with the abovementioned rules.
- PK data: For PK data the arithmetic mean, standard deviation, median, minimum, maximum, coefficient of variation (CV%), geometric mean and geometric coefficient of variation (geo CV%) values will be presented. For the ratio of concentration data to the (within 30 minutes) pre-dose concentration on Day 1, the  $\ln(\text{SD}^*)$  will also be presented.
- Categorical variables: Descriptive statistics will include frequency counts and percentages per category. Percentages will be rounded to one decimal place, with the denominator being the number of subjects in the relevant population with non-missing data, unless otherwise specified.
- Time to Event Analysis: Through the Kaplan-Meier method, nonparametric estimates of the survivor function will be represented by quartile estimates (Q1, Median and Q3) along with 95 CIs. Product limit estimates will be presented as part of appendices to the study outputs (SAS output).
- Imputation: No missing data will be imputed.
- Baseline: Baseline values will be defined as the last valid, non-missing observation for each subject prior to the first dose of study medication. For the PK analysis, baseline will be defined as the pre-dose value for each study day.
- Repeat assessments (Safety): No repeat assessments will be included in summary presentations (Tables, Figures). Only the original values will be used in summary presentations. All repeat assessments captured in the Electronic Data Capture (EDC) system will be presented in the data listings.
- Assessment windows: All assessments will be included in the data listings and no visit windows will be applied to exclude assessments that were performed outside of the protocol specified procedure windows.
- Date and time display conventions: The following display conventions will be applied in all outputs where dates and/or times are displayed:
  - o Date only: DDMMMYYYY
  - o Date and time: DDMMMYYYY /HH:MM

If only partial information is available, unknown components of the date or time will be presented as 'NK' (not known), i.e., '2016-NK-NK'. Times will be reported in military time.

In the summary tables and figures, treatment groups will be summarized separately for SD/MAD, each cohort, combined placebo and overall (all subjects). Study outcomes will be summarized as follows:

- For each active dose level (overall):
  - o SD Phase:
    - rhu-pGSN 6 mg/kg
    - Placebo
    - Overall
  - o MAD Phase
    - rhu-pGSN 6 mg/kg
    - rhu-pGSN 12 mg/kg
    - rhu-pGSN 24 mg/kg
    - Combined Active
    - Combined Placebo
    - Overall

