Doses in the multiple-dose arms should be given at 24-hour (\pm 60-minute) intervals. For the one dose in the SD arm and the first 2 doses in the multiple-dose arms, blood will be drawn within 30 minutes predose, and 5-10 minutes after the end of administration, as well as 2, 8, 12 and/or 16, and 24 hours after the end of administration (\pm 30 minutes) for analysis of plasma for maximum concentration (C_{max}), time to maximum concentration (T_{max}), terminal half-life ($T_{1/2}$), area under the curve from time zero to 8 hours (AUC_{0-8}), and area under the curve from time zero to infinity (AUC_{inf}). Sampling at both the 12- and 16-hour time points is encouraged where feasible, but only one of these two times is required. Identical PK sampling is encouraged on Day 3 where feasible, but not required in the multiple-dose arms. In the multiple-dose arms, the sample at 24 hours after the prior dose must be drawn before the next dose is given and can serve as the predose sample for the next dose as long as administered within the subsequent 30 minutes.

The syringe, filter, and extension tubing should be connected after disconnecting the IV as close to the patient as possible. On Day 28, collect samples for analysis of pGSN levels and antibodies against pGSN.

Number of subjects (enrolled):

A total of 32 (6 rhu-pGSN and 2 placebo recipients per dose cohort x 4 dosing levels)

Major inclusion criteria:

1. Age ≥ 18 years

2. Gender: either
3. Informed consent obtained from subject
4. Domicile: home, assisted living, rehabilitation facility, or nursing home (as long as the prospective participant is capable of providing written informed consent)
5. Duration of infection precipitating hospitalization by history <14 days
6. Planned or actual admission to hospital with a primary diagnosis of CAP within 24 hours of presentation to the hospital
7. Primary admitting diagnosis of pneumonia supported by a compatible clinical presentation with a documented infiltrate consistent with pneumonia on chest radiograph or CT, as assessed by the admitting emergency-department (ED), clinic, or ward physician or equivalent caregiver
 - Recommended (not mandatory) guidance/discretionary criteria defining patients with CAP:
 - At least 2 symptoms: difficulty breathing, cough, production of purulent sputum, chest pain
 - At least 2 vital sign abnormalities: fever, tachycardia, tachypnea

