5.2.2. Secondary Endpoints

- PK for rhu-pGSN including, but not limited to maximum concentration (C_{max}), time to maximum concentration (T_{max}), terminal half-life ($T_{1/2}$), area under the curve from time zero to 8 hours (AUC_{0-8}), area under the curve from time zero to infinity (AUC_{inf}) (levels measured within 30 minutes predose, 5-10 minutes after the end of administration, and 2, 8, 12 and/or 16, and 24 hours (\pm 30 minutes) after each dose (Day 3 sampling in multiple-dose arms is optional)

- Incidence, causality, and severity of AEs and SAEs graded according to the NCI CTCAE version 4.03 (or equivalent); clinically significant laboratory and/or EKG abnormalities as required by SOC; death irrespective of cause; cause of death per investigator, including relationship to study drug; use of vasopressors, intubation, or transfer to the ICU or equivalent through Day 28 (secondary time point)

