- ^d Doses in the multiple-dose arms should be given at 24-hour (\pm 60-minute) intervals. Blood for PK will be drawn within 30 minutes predose, 5-10 minutes after the end of administration, and 2, 8, 12 and/or 16, and 24 hrs (\pm 30 minutes) after the end of administration. Sampling at both the 12- and 16-hour time points is encouraged where feasible, but only one of these two times is required. In the multiple-dose arms, the sample at 24 hours after the prior dose must be drawn before the next dose is given and can serve as the predose sample for the next dose as long as administered within the subsequent 30 minutes. Samples are spun and plasma frozen and sent to a central lab for analysis.
- ^e Identical blood collection for PK analysis is encouraged on Day 3 but not required. Where feasible, the last PK sample would occur on Day 4 (i.e., 24 hours after the end of administration on Day 3); otherwise, because there is no study drug administered after Day 3, no further PK sampling would be done on Day 4. Samples are spun and plasma frozen and sent to a central lab for analysis.
- ^f A 10-mL aliquot (equal parts serum and plasma) will be frozen for subsequent biomarker analysis including, but not limited to, procalcitonin, pGGSN, TNF α , TGF β , IL1 β , IL1 α , IL2, IL4, IL6, IL10, IL17a levels and sent to a central lab for analysis.
- ^g Sample to be sent to a central lab for analysis.
- ^h Subjects are to be monitored for administration site reactions during study drug administration and for 1 hour after its completion.
- ⁱ The third dose of study drug may be given in a monitored outpatient setting where appropriate.
- ^j Day 1 is the first day of study treatment. Baseline tests (including blood draws) should be performed prior to administration of the first dose.
- ^k Test/assessment does not have to be repeated if performed within the prior 36 hours unless dictated by standard of care.

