## 9. PHARMACOKINETICS (PK)

All PK summary tables and figures will be based on the PK Population. All listings will be based on the Safety Population (Actual Treatment). All analyses will be done by treatment group.

For the 1 dose in the SD arm and the first 2 doses in the MAD arms, blood will be drawn within 30 minutes pre-dose, and 5-10 minutes after the end of administration, as well as 2, 8, 12 and/or 16, and 24 hours after the end of administration ( $\pm$  30 minutes) for analysis. Identical PK sampling is encouraged on Day 3 where feasible (but not required) in the multiple-dose arms.

In this section (section 9):

- The rhu-pGSN treatment group will be referred to the Active treatment group.
- Exogenous pGSN concentrations will be referred to as rhu-pGSN concentrations.
- Endogenous pGSN + Exogenous pGSN (total) will be referred to as pGSN

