#### Ratio of Plasma pGSN

For subjects that do not have quantifiable pre-dose concentration values on each day, the pre-dose value will be set to  $\frac{1}{2}$  lower limit of quantification (LLQ).

Individual plasma pGSN: Day 1, 2 and Day 3 pGSN concentration ratios from each day's pre-dose will be summarized by nominal sampling time.

Plasma pGSN concentrations that are below the quantitation limit (BQL) will be set to  $\frac{1}{2}$  the lower level of quantification post dose for calculation of summary statistics for concentration ratio data at each time point.

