#### Analysis of Estimated rhu-pGSN

This analysis will exclude the placebo treatment group:

- Pre-dose values on each study day will be presented as recorded;
- Pre-dose values on each study day that are BLQ will be set to  $\frac{1}{2}$  LLQ;
- Subsequent BLQ values (post the first quantifiable concentration on each day) will be set to  $\frac{1}{2}$  LLQ.
- Estimated rhu-pGSN concentration  
= concentration on Day z at Time Point y – Day z Pre-dose concentration

Individual estimated rhu-pGSN concentrations will be summarized by nominal sampling time. Geometric summary statistics will not be calculated for estimated rhu-pGSN concentrations, as these values could be lower than or equal to 0.

Estimated Individual (for each subject) and mean estimated plasma rhu-pGSN concentration over time will be displayed graphically in linear plots of estimated rhu-pGSN concentration versus time. The actual collection time will be used for individual estimated plasma rhu-pGSN concentration curve and the nominal time will be used for plot of mean estimated plasma rhu-pGSN concentration curve.

Estimated plasma concentrations vs. time data will be analyzed using SAS software. Actual collection time will be used in the calculation of plasma PK parameters. The following parameters (including dose normalized parameters) will be calculated for each study day:

- $AUC_{0-t}$
- $AUC_{0-8h}$
- $C_{max}$

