#### Double Delta Analysis of Estimated rhu-pGSN

- Pre-dose values on each study day will be presented as recorded;
- Pre-dose values on each study day that are BLQ will be set to  $\frac{1}{2}$  LLQ;
- Subsequent BLQ values (post the first quantifiable concentration on each day) will be set to  $\frac{1}{2}$  LLQ.
- Estimated rhu-pGSN will be calculated as follows:  
= (Active Treatment Group Concentration on Day z at Time Point y – Day z Pre-dose Concentration) - (Mean Placebo Treatment Group Concentration on Day z at Time Point y – Mean Placebo Day z Pre-dose Concentration)

Estimated rhu-pGSN concentrations will be summarized by nominal sampling time. Geometric summary statistics will not be calculated for estimated rhu-pGSN concentrations, as these values could be lower than or equal to 0.

Estimated Individual (for each subject) and mean estimated plasma rhu-pGSN concentration over time will be displayed graphically in linear plots of estimated rhu-pGSN concentration versus time. The nominal time will be used for individual estimated plasma rhu-pGSN concentration curve and the nominal time will be used for plot of mean estimated plasma rhu-pGSN concentration curve.

Estimated rhu-pGSN plasma concentrations vs. time data will be analyzed using SAS software. Nominal time will be used in the calculation of plasma PK parameters. The following parameters (including dose normalized parameters) will be calculated for each study day:

- $AUC_{0-t}$
- $AUC_{0-8h}$
- $C_{max}$

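### On MAD Days 2–3, subtracting the same day's pre-dose value removes carried-over drug: with endogenous pGSN stable or correctly placebo-adjusted, estimated rhu-pGSN understates total exogenous exposure and cannot show accumulation

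*SAP*

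**What the plan says.** SAP Section 9 defines the target: "Exogenous pGSN concentrations will be referred to as rhu-pGSN concentrations". SAP Section 3 sets the reference: "For the PK analysis, baseline will be defined as the pre-dose value for each study day".

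SAP Section 9.2 applies that reference in two estimators, each feeding AUC0-t, AUC0-8h and Cmax (with dose-normalised forms) for every study day:

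- Single delta: "concentration on Day z at Time Point y – Day z Pre-dose concentration".
- Double delta: the same active-arm difference, minus the placebo mean at that time point less the "Mean Placebo Day z Pre-dose Concentration".

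The ratio analysis follows the same rule, summarising "Individual plasma pGSN: Day 1, 2 and Day 3 pGSN concentration ratios from each" day's pre-dose value.

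On sampling, the Protocol synopsis says that in the multiple-dose arms "the sample at 24 hours after the prior dose must be drawn before the next dose is given". Protocol Table 6, footnote d, adds that this sample "can serve as the predose sample for the next dose as long as administered within the subsequent 30 minutes". Day 3 PK sampling is optional.

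The secondary endpoint (Protocol 5.2.2) is "PK for rhu-pGSN including, but not limited to maximum concentration", with AUC0-8 and AUCinf also named.

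The reference day is not consistent within the SAP:

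- In Section 9.1 the Cmax row uses each study day's pre-dose value, while the DN_Cmax row uses the Day 1 pre-dose value.
- Section 3 mentions a ratio to the Day 1 pre-dose concentration, while Section 9.2 takes ratios to each day's.
- The mock MAD listings of individual total pGSN and of estimated rhu-pGSN (16.2.6.2.2) carry Day 1 reference headings.

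**The concern.** The stated target is exogenous protein. On Day 1 the pre-dose sample is purely endogenous, so subtracting it isolates drug. On Days 2 and 3 of the MAD cohorts the pre-dose sample is endogenous pGSN plus whatever remains of earlier doses, and the formula removes both. Placebo subjects never carried drug, so the double delta corrects endogenous drift only.

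The PK profile after single or multiple doses is the secondary objective, and these are the only AUC and Cmax summaries with endogenous pGSN removed. A reader comparing Day 3 with Day 1 would see flat Cmax and flat or falling AUC even if exposure were rising. Separately, with Cmax and DN_Cmax on different references, DN_Cmax is not the tabulated Cmax divided by dose, which is its own definition.

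**Working it through.** The documents give no figure to reproduce, so this is a model check.

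**Inputs.** Three equal daily doses 24 h apart (Protocol 6.3 and Table 6). Assumed: linear one-compartment kinetics, and endogenous pGSN stable or exactly removed by placebo. No human plasma half-life is in the available text, so a range is assumed. The 10 to 16 h in Protocol 4.4.1 is radioactivity in animal lung after pulmonary exposure and is not used as an input.

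**Formulas.** Scale each dose to a peak of 1. Let k = ln 2 / half-life, r = exp(−24k), and residual R = r on Day 2 or r + r² on Day 3. Let I(T) = (1 − exp(−kT))/k.

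- True Cmax = 1 + R. SAP Cmax = (1 + R) − R = 1.
- True AUC0-T = (1 + R) × I(T). SAP AUC0-T = (1 + R) × I(T) − T × R.

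**Example, 12 h.** k = 0.0578, r = 0.25, I(8) = 6.41, I(24) = 12.98.

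- Day 2, R = 0.25: Cmax 1/1.25 = 0.80. AUC0-8 true 8.01, SAP 8.01 − 2.00 = 6.01, ratio 0.75.
- Day 3, R = 0.3125: Cmax 1/1.3125 = 0.76. AUC0-24 true 17.04, SAP 17.04 − 7.50 = 9.54, ratio 0.56.

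**Results.**

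| Assumed half-life (h) | 4 | 6 | 8 | 12 | 16 |
|---|---|---|---|---|---|
| r | 0.016 | 0.063 | 0.125 | 0.250 | 0.354 |
| Day 2 AUC0-8, estimated/true | 0.97 | 0.91 | 0.85 | 0.75 | 0.69 |
| Day 2 Cmax, estimated/true | 0.98 | 0.94 | 0.89 | 0.80 | 0.74 |
| Day 3 AUC0-8, estimated/true | 0.97 | 0.90 | 0.83 | 0.70 | 0.62 |
| Day 3 Cmax, estimated/true | 0.98 | 0.94 | 0.88 | 0.76 | 0.68 |
| Day 3 AUC0-24, estimated/true | 0.93 | 0.82 | 0.71 | 0.56 | 0.48 |
| True Day 3/Day 1 (all three) | 1.02 | 1.07 | 1.14 | 1.31 | 1.48 |
| SAP Day 3/Day 1, AUC0-24 | 0.95 | 0.87 | 0.81 | 0.73 | 0.71 |
| SAP Day 3/Day 1, Cmax | 1.00 | 1.00 | 1.00 | 1.00 | 1.00 |

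These are exact integrals. The log-down trapezoid at the planned sample times gives a larger loss: Day 3 AUC0-24 at 0.87–0.91 (4 h), 0.74–0.79 (6 h), 0.52–0.54 (12 h) and 0.45–0.47 (16 h).

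**As a per-dose increment.** The right values are then 1 for Cmax and I(T) for AUC. SAP Cmax is correct. SAP AUC is I(T) − R × (T − I(T)), which is below I(T) for any R > 0 because T exceeds I(T). The residual decays through the day but is subtracted as a constant.

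**If endogenous pGSN recovers.** Suppose it rises linearly by 25% of the Day 1 peak increment over 72 h. At 4 h the true Day 3 AUC0-24 is 5.77 and the residual subtraction is 24 × 0.0159 = 0.38.

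- Same-day single delta: recovery adds 24 × (0.25/3)/2 = 1.00, so the ratio is (5.77 − 0.38 + 1.00)/5.77 = 1.11, too high.
- Single delta from Day 1 pre-dose: recovery adds 24 × 0.25 × (2/3 + 1)/2 = 5.00, so the ratio is (5.77 + 5.00)/5.77 = 1.87. At 12 h it is (17.04 + 5.00)/17.04 = 1.29.

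**The two double deltas under imperfect placebo matching.** Suppose treated subjects recover more than placebo by 10% of the Day 1 peak increment at 72 h. This adds 24 × (0.10/3)/2 = 0.40 to the same-day version and 24 × 0.10 × (2/3 + 1)/2 = 2.00 to the Day 1 version. Net error in Day 3 AUC0-24:

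| Assumed half-life (h) | 4 | 6 | 8 | 12 |
|---|---|---|---|---|
| Same-day double delta (SAP) | 0% | −14% | −26% | −42% |
| Day 1 double delta | +35% | +23% | +17% | +12% |

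**Placebo noise in the Day 1 version.** With an assumed SD of 10% of the Day 1 peak increment for the placebo change, the added standard error is 24 × 0.10/√n over true AUC0-24. At 12 h it is 6% (n = 6) or 8% (n = 3); at 4 h, 17% or 24%.

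**The case against.** The same-day reference looks deliberate. Section 3, all of Section 9.2 and most rows of Section 9.1 use it, and it limits the multi-day endogenous drift that enters the estimate. That drift is plausible, since Protocol 4.3 describes reduced levels being restored after healing. As a same-day increment Cmax is right. The estimated values are additional to the total-pGSN parameters, which still show accumulation, though mixed with endogenous protein. At a half-life near 4 h the loss is small, and a Day 1 reference can do worse.

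Most of this stands, and it limits the remedy. It does not rescue the estimate as labelled: the SAP calls it exogenous pGSN, not an increment, and AUC is too low even as an increment if drug remains.

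Four stronger readings are tempting and are not supported:

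- That the estimates are always too low. The direction requires stable or correctly adjusted endogenous pGSN; the 1.11 above is a counterexample for the single delta.
- That a particular size of error is established. No human plasma half-life is in the available text, and part of Protocol 4.4.2 was not available to this review, so one may be stated there.
- That dose escalation is compromised. No stated escalation rule uses these values.
- That the listings prove a Day 1 reference was intended. The heading in Listing 16.2.6.2.2 may be a template carry-over: it also appears in the single-dose listing, and its Day 2 pre-injection cell is blank, where a Day 1-referenced change would have a value.

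**Conclusion.** The point holds, conditionally. On MAD Days 2–3 the planned estimate of exogenous pGSN discards carried-over drug. With endogenous pGSN stable or correctly placebo-adjusted, it understates total exogenous Cmax, AUC0-8 and AUC0-t whenever drug remains at 24 h, and it cannot show accumulation.

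Under the one-compartment model, with assumed half-lives of 4 to 16 h, the loss in Day 2 AUC0-8, which has required sampling, runs from 3% to 31%. The loss in Day 3 AUC0-24, which has optional sampling, runs from 7% to 52%. The same-day ratios shrink for the same reason.

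Day 1, the single-dose arm, the total-pGSN parameters and the biomarker summary of pGSN (which uses a pre-first-dose baseline) are unaffected. The harm is to reported secondary PK results. The conflict over the reference day needs correcting whatever the half-life.

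**What to change.** For Days 2–3, add a double delta referenced to the Day 1 pre-dose value in both arms: each active subject's change from Day 1 pre-dose, minus the mean change from Day 1 pre-dose among MAD placebo subjects sampled at that time point. Show the placebo n. Derive AUC0-t, AUC0-8, Cmax and their dose-normalised forms from it.

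Report it beside the same-day version without prescribing which leads. Label the Day 1 version as total exogenous exposure, the one to read for accumulation. Label the same-day version as an increment whose AUC is biased low when drug remains. Do not use a Day 1 single delta alone, because it counts endogenous recovery as drug.

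Make the reference day consistent across SAP Sections 3, 9.1 and 9.2 (including both ratio analyses), the Day 2–3 table shells (14.2.1.2, 14.2.1.3, 14.2.1.5, 14.2.1.6, 14.2.3.2, 14.2.3.3), the Day 2–3 pages of Figures 14.2.2.1, 14.2.2.2, 14.2.4.1 and 14.2.4.2, and Listings 16.2.6.2.2 and 16.2.6.4.2.

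The cost is SAP text, shells and programs; no new data are needed. The Day 1 double delta rests on at most 6 MAD placebo subjects (3 cohorts × 2), possibly fewer on Day 3, and assumes similar endogenous recovery in treated and placebo subjects. Around a 4 h half-life it can be less accurate than the same-day version, which is why both should be shown.
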